4.1 General Concomitant Medication and Supportive Care Guidelines

For VLNT, the following is routinely used pre-operatively (standard of care, SOC):

Chlorhexidine gluconate scrub.

Anesthesia risks (anesthesia and intubation) (SOC for VLNT placement; research for BioBridge placement):

Intubation injury; aspiration; anesthesia awareness; difficulty breathing after surgery; malignant hyperthermia; reaction to anesthesia drugs; nausea; vomiting; dry mouth; sore throat; shivering; sleepiness; confusion; hoarseness.

For VLNT, the following medications are routinely used intra-operatively (SOC for VLNT placement; research for BioBridge placement):

Midazolam; fentanyl; lidocaine; propofol; rocuronium; dexamethasone; ketamine; hydromorphone; acetaminophen; ondansetron; antibiotic (usually cephalexin unless allergic); scopolamine; magnesium; IV fluids (saline, lactated ringers).

Arterial line risks (SOC): Bleeding; hematoma; thrombosis; infection.

Rare risks: permanent arterial occlusion; pseudoaneurysm, sepsis.

Surgical risks (SOC for VLNT placement; research for BioBridge placement):

Bleeding; deep vein thrombosis (DVT); delayed healing; death; infection; injury during surgery; medical complications (pneumonia; MI; CVA; itching; scarring; numbness; neurovascular injury; tingling around surgical site(s); pain; persistent edema; seroma; flaps loss; donor site lymphedema; bruising; and need for reoperation.

For VLNT, the following medications are routinely used post-operatively (SOC):

Oxycodone; aspirin; ondansetron; Bacitracin zinc ointment; Lovenox; hydromorphone; heparin infusion

Lymphoscintigraphy (SOC for VLNT placement; research for BioBridge placement):

LSG will be performed for both research purposes and standard of care (1-2 scans pre-surgery and 1 to 2 scans 12 months post-surgery).

Lymphoscintigraphy requires four injections of 250uCi Sulfur Colloid, is performed at baseline and 12 months after surgery, and involves exposure to radiation. The LSG for research are not necessary for medical care. The additional amount of radiation exposure is about 7 mSv, which is approximately equal to 14% of the limit that radiation workers (for example, a hospital X-ray

technician) are allowed to receive in 1 year. This amount of radiation involves minimal risk and is necessary to obtain the research information desired.

Because the doses of radiotracer administered are small, diagnostic nuclear medicine procedures result in relatively low radiation exposure to the patient and the radiation risk is low. Nuclear medicine diagnostic procedures have been used for more than 5 decades, and there are no known long-term adverse effects from such low-dose exposure. Allergic reactions to radiopharmaceuticals may occur but are extremely rare and are usually mild. Injection of the radiotracer can be painful and may cause redness which should rapidly resolve.

Technetium 99m sulfur colloid is a nuclear imaging agent. The most frequently reported adverse reactions include rash; allergic reaction; hives; allergic shock; and low blood pressure. Less frequently reported adverse reactions are fatal cardiopulmonary arrest; seizures; shortness of breath; wheezing; abdominal pain; flushing; nausea; vomiting; itching; fever; chills; perspiration; numbness; and dizziness. Local injection site reactions; including burning; blanching; redness; swelling; and scarring, have also been reported.

ICG fluorescence lymphatic mapping (SOC, at baseline and 12 months post-surgery)

ICG (indocyanine green) is a water-soluble tricarbocyanine dye, has a short plasma half-life of 3 to 5 minutes in humans, is excreted exclusively by the liver into the bile, and is not associated with risk for nephrotoxicity. ICG contains sodium iodide and is contraindicated in patients with iodine hypersensitivity. Anaphylaxis or other allergic reactions may occur.

Skin punch biopsy (research):

Skin biopsies of affected limb will be performed at baseline and at 12 months following surgery (optional for control group). Potential side effects include pain, infection and bleeding. Participants will receive 48 hours of prophylactic oral antibiotic to mitigate the potential for infection. Bleeding should be minimal as only a 6 mm biopsy lesion will be utilized. Each incision is closed with one suture.

For biopsy, xylocaine with epinephrine:

Xylocaine with epinephrine is used as a local anesthetic. Potential risks include: feeling anxious; shaky; dizzy; restless; or depressed; drowsiness; vomiting; ringing in your ears; blurred vision; confusion; twitching; seizure (convulsions); fast heart rate; rapid breathing; feeling hot or cold; weak or shallow breathing; slow heart rate; weak pulse; or feeling like you might pass out. Less serious side effects include: mild bruising; redness; itching; or swelling where the medication was injected; mild dizziness; nausea; numbness in places where the medicine is accidentally applied.

For biopsy, cephalexin (unless allergic to this antibiotic):

Cephalexin is an antibiotic. Possible adverse effects include the following:

- Central nervous system: Agitation, confusion, dizziness, fatigue, hallucinations, headache
- Dermatologic: allergic swelling, severe rash, Stevens-Johnson syndrome, toxic epidermal necrolysis, hives
- Gastrointestinal: Abdominal pain, diarrhea, stomach burning, gastritis, nausea , colitis, vomiting
- Genitourinary: Genital itching, genital thrush, vaginitis, vaginal discharge
- Hematologic: elevated white blood cell counts
- Hepatic: abnormal liver function, jaundice , transient hepatitis
- Neuromuscular & skeletal: joint aching and swelling, joint disorder
- Renal: kidney inflammation
- Miscellaneous: Allergic reactions

Phlebotomy (SOC and research):

Risks of blood samples being drawn include: pain; bruising; bleeding; inflammation; infection; temporary redness of the skin where the injection is given; and light headedness. Care will be taken to avoid these difficulties.

Bioimpedance spectroscopy (BIS) (research):

Placement of and/or removing the pads may cause skin irritation; BIS analysis is painless.

Calipers (research):

The calipers may cause some discomfort due to the pinching of the skin.

Stanford Experience

[name] has performed more than 100 cases of VLNT over the last 5 years. The average volume reduction is 55 to 65%. There has not been any flap loss. There is < 5% post-operative infection; < 5% wound dehiscence; 2% of seroma; 2% of hematoma; 1% post-operative deep vein thrombosis (DVT). There have had no major complications. To date, there has been no incidence of donor site lymphedema. In general, this is a well-tolerated operation. The positive outcome is, in part, dependent upon patient compliance with postoperative instructions.

4.2 Criteria for Removal from Study

It will be documented whether or not each subject completed the clinical study. Subjects who discontinue from the study early will be asked to return for a final study visit within the 4 weeks following the decision to withdraw. If a subject withdraws, all efforts will be made to complete

and report the observations, particularly the follow-up examinations, as thoroughly as possible. A sincere effort will be made to contact subject either by telephone, letter, email, to determine the reason why they failed to return for the necessary visits or withdrew from study, and reason(s) will be documented.

Reasons that a subject may discontinue participation in a clinical study may include the following:

- Intercurrent illness that prevents continuation in study
- Potential health hazard to patients, as indicated by the incidence or severity of AEs
- The subject may choose to withdraw from the study at any time for any reason
- General or specific changes in the patient's condition that render the subject unacceptable for further treatment in the judgment of the investigator
- Severe non-compliance to protocol as judged by the investigator
- Death
- Closure of study

4.3 Alternatives

Alternatives to participation in this trial include enrollment in VLNT without the addition of the BioBridge scaffold or standard of care treatments for lymphedema. These include, but are not limited to, compression sleeves or compression devices, decongestive therapy, intermittent pneumatic compression devices. In general, there are 4 types of surgical intervention for lymphedema, as follows.^{35,36,46-48}

Lymphatic Microsurgical Preventive Healing Approach (LYMPHA), aimed at lymphedema prevention, was developed at the University of Genoa.^{37,38} At the time of axillary lymph node dissection, a lymphaticovenous anastomosis (LVA) is performed to restore lymphatic flow. While a comparatively new procedure, for patients undergoing ALND, results have been very promising.³⁹ However, since it is aimed at lymphedema prevention, LYMPHA is not an appropriate alternative for this participant population, since inclusion into this trial requires a diagnosis of lymphedema.

Excisional surgery, suction-assisted protein lipectomy (SAPL), pioneered by [name], is performed for chronic non-pitting lymphedema. SAPL is highly effective at removing the excess solid tissue (hypertrophied adipose tissue) but does not restore lymphatic function. [name], who trained with [name], frequently performs this procedure. Post-operatively, the continuous use (24 hours/day, 7 days/week) of custom compression garments is required. These may need to be frequently replaced in the 1st year after the procedure. Maintenance of reduction is dependent on patient compliance with continuous compression garment use.⁴⁰ SAPL is also not an appropriate alternative, since its aim is removal of excess tissue and not the restoration of lymphatic function.

Microvascular reconstruction with LVA is also performed by [name]. A large study, by Chang, *et al*, noted that LVA, is most effective in early stage lymphedema of the upper extremity. Early volume reduction may be seen in the first postoperative week but maintenance of response is unknown due to short follow-up.⁴¹ Additionally, LVA may not enhance the regional immune impairment that accompanies lymphedema.

Tissue transfer, ie, vascularized lymph node transfer (VLNT), when successful, is intended to optimally restore both lymphatic circulatory and immune function. The BioBridge scaffold has been designed, and tested in preclinical animal models, to optimize the surgical outcome specifically in vascularized lymph node transfer. It is this surgical intervention that is under specific investigation in this protocol.

5. INVESTIGATIONAL AGENT/DEVICE/PROCEDURE INFORMATION

5.1 Investigational Agent/Device/Procedure

Complete information about the investigational device can be found in the Investigator's Brochure and IDE document.

The BioBridge Collagen Matrix is a sterile implantable biocompatible and biodegradable surgical mesh ribbon comprised of highly purified porcine collagen that is designed to provide mechanical support and repair for weaknesses and deficiencies in soft tissue. The device was cleared by CDRH Division of Surgical Devices on 8 January 2016 under 510(k) K151083 for use as a collagen-derived surgical mesh for plastic and reconstructive surgery. For the purposes of this investigation, the commercially-available device will not be altered or modified in any way.

The collapsed ribbon structure of BioBridge is comprised of a single sheet of cross-linked collagen collapsed into multiple folds forming a thin membrane with aligned collagen fibrils in the same lengthwise direction. This scaffold structure provides mechanical properties that contribute to strong tensile strength, which provides support to weaknesses and deficiencies in soft tissue and aids in bridging a connection between two healthy soft tissues.

BioBridge is fabricated using a proprietary manufacturing process that produces a narrow and very thin ribbon-like membrane comprised of aligned collagen fibrils, creating a multi- luminal structure that can be sutured, and provides the desired mechanical properties for support of soft tissue repair. This approach presents the opportunity to enable the use of highly purified collagen, in a defined structure that has mechanical properties similar to those of the predicates, but without undesirable telopeptides found in collagen matrices derived from animal dermis. The smaller ribbon-like form factor also gives the surgeon greater flexibility for minimally invasive delivery and to tailor their procedures to better address a specific patient need, where one or more BioBridge devices can be implanted depending on the surgeon's discretion.

Fibralign sources the highly purified Type I porcine-derived collagen from a FDA registered and ISO-qualified supplier. Fibralign employs a proprietary manufacturing process that takes highly purified Type I porcine-derived collagen and produces narrow, ribbon-like membranes

comprised of highly aligned collagen fibrils that mimic desired mechanical properties found in natural extracellular matrices. A chemical crosslinking agent, known as EDC [N-ethyl-N'-(3 -dimethylaminopropyl)carbodiimide], is used during the manufacturing process to promote the crosslinking of the collagen but the crosslinker itself is not added to nor bound to the collagen matrix. The crosslinker residuals are water soluble and are removed by product rinsing at the end of the production process. The final product is packaged into individual storage tubes and then sealed in a multi-pack and terminally sterilized.

BioBridge is fabricated using a proprietary manufacturing process that collapses a single sheet layer along the width direction to form a scaffold, comprised of collagen fibrils (see Figure 1).

[figure not shown]

Figure 1. BioBridge (250x magnification)

[figure not shown]

Figure 1. BioBridge Collagen Matrix.

BioBridge has a thickness in a range of 0.10 mm to 1.0 mm, and the device is available in lengths over 1500 mm.

Extensive safety and performance testing has been completed for BioBridge in support of the 510(k) clearance, including biocompatibility and degradation studies, as well as full material characterization of the collagen content and manufacturing reagents used in fabricating BioBridge (provided as part of the 510(k) submission). Significant efforts have been made in sourcing materials, product design and device manufacturing to minimize potential risks associated with the device.

These include:

- 1) BioBridge is made of highly-purified, pepsin-treated porcine Collagen Type I. The material is sourced from Datum Dental, which is referenced in the FDA 510(k). The same material is used in ColBar Ossix and ColBar Ossix Plus which have 510(k) clearance and CE mark and been used in over 350,000 implant procedures worldwide. Porcine-derived collagen matrix products have a long history of safe use as a surgical support device where the physical construct of the implant can provide a bridging material to support a desired surgical outcome. This same type of collagen is commonly used in very sensitive applications like dura layers involving the spinal cord and brain.
- 2) BioBridge is manufactured from this highly purified collagen in a GMP cleanroom facility under Class-100 hoods with upmost care and then e-beam sterilized after packaging. This has been supported by shelf life age testing and sterilization validation.
- 3) The BioBridge matrix is a very narrow ribbon, a thread-like structure that has a similar form factor to suture. In practice, the proposed treatment involves a very small amount of bulk material (10 mg/device, with 4 to 10 devices/patient) being implanted subcutaneously.
- 4) BioBridge has been shown to be biologically more inert than catgut suture, which is being commonly used in the surgical procedures proposed in the study. This was demonstrated in four GLP implantation studies that were performed in support of the 510(k) application. The subcutaneous implantation studies (2, 13 and 26 week) have shown that BioBridge was considered non-irritant and determined to have less inflammatory reaction than the control articles (catgut suture). These implantation studies have also shown that BioBridge integrates well and safely absorbs in subcutaneous tissue in 6 to 9 months.
- 5) Based on review of approved surgical meshes and earlier testing of BioBridge, it is not anticipated that implanting this small amount of purified collagen into this treatment area will create additional complications to the damaged lymphatic tissue. None of BioBridge's predicate devices have counter indications for use with patients that have lymphedema. A further review of the larger surgical mesh devices that are made of extracellular matrix and widely used in breast reconstruction surgical procedures for similar patients also did not show any contraindications for lymphedema. Preliminary results from the Dominican Republic pilot study provide assurance about this safety, no complications have been reported to date with 55 devices implanted in 8 subjects. Furthermore, in the preclinical

large animal lymphedema study, there were neither overt complications nor any histological evidence of significant inflammatory reaction or other complications observed with the 120 devices implanted.

- 6) In this proposed treatment, BioBridge is not intended to replace normal body structure or provide full mechanical strength. The device will be implanted in the surgical area during transplantation in subcutaneous soft tissue and not intended to come in direct contact with damaged lymphatic vessels. Even if the device ends up not providing the mechanical function as intended (fails), it is not expected to be catastrophic or to materially impact the subject. If a failure occurs, the surgical outcome would be expected to be the same as the control group receiving the ALNT procedure without the device, which is the current standard of care for lymphedema patients.

5.2 Availability

The investigational device will be provided by Fibralign Corporation. It will be ordered specifically for each subject and will be shipped directly to the PI/Co-PI.

5.4 Agent Accountability

The investigational device will be stored in secure location. Only authorized OR staff and study staff will have access to this device. Study investigators will perform accountability.

6. DOSE MODIFICATIONS

N/A (device)

7. ADVERSE EVENTS AND REPORTING PROCEDURES

7.1 Potential Adverse Events

BioBridge is contraindicated for use in any patient with known sensitivity to porcine products. Possible adverse reactions may include, but not limited to contamination, infection, inflammation, allergic reaction, adhesions, and tissue encapsulation. If infection or allergic reaction occurs, the entire matrix may have to be revised or removed.

From October 2015 to Oct 2016, a pilot study was conducted in the Dominican Republic. A total of 55 BioBridge threads were implanted into 8 participants with no reported complications

(Hadamitzky, 2016.⁴³ Personal communication, Drs [name] and [name], 4 April 2017).

Physical exam will be performed at study visits to assess patient safety. Additionally, the subjects will have direct contact information for use 24 hours/day, 7 days/week to report concerning symptoms. Adverse events will be reported as below.

7.2 Adverse Event Reporting

Adverse events will be graded according to CTCAE v5. Both Serious and Non-Serious Adverse Events will be clearly noted in source documentation and listed on study specific Case Report Forms (CRFs). The Protocol Director (PD) or designee will assess each Adverse Event (AE) to determine whether it is unexpected according to the Informed Consent, Protocol Document, or Investigator's Brochure, and related to the investigation. All Serious Adverse Events (SAEs) will be tracked until resolution, or until 30 after the last dose of the study treatment.

SAEs CTCAE Grade 3 and above, and all subsequent follow-up reports will be reported to the Stanford Cancer Institute Data and Safety Monitoring Committee (DSMC) using the study specific CRF regardless of the event's relatedness to the investigation. Following review by the DSMC, events meeting the IRB definition of 'Unanticipated Problem' will be reported to the IRB using e-Protocol within 10 working days of DSMC review, or within 5 working days for deaths or life-threatening experiences.

7.3 Stopping Rule

The study will be terminated if more than 1 of the first 10 subjects experience an infection related to the BioBridge device. If, after the first 10 subjects are treated, a rate > 10% of BioBridge-related infections is observed, accrual will be paused for a safety review. The Stanford Cancer Institute (SCI) Data Safety Monitoring Committee (DSMC) will be informed of any such review.

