3.4 Randomization Procedures

We will use a blocked randomization design. Approximately 60 subjects will be randomized in a 4:1 ratio to the intervention arm (VLNT + BioBridge): control arm (VLNT alone). Randomization will be done within blocks (of size 5) so that the balance between treatments is preserved throughout the trial, where A = VLNT/Biobridge and B = VLNT alone.

The order in which these blocks will be assigned to the enrolled subjects will be prospectively, independently determined through a random number generator function.

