VLNT, 2 groups; one with BioBridge scaffold (intervention group), one VLNT only (control group), will occur between S3 and T1 visits.

T1 (3 months following surgery): physical exam, measurements, LymQoL survey, medication and symptom/AE review, VS, weight.

T2 (6 months following surgery): physical exam, measurements, LymQoL survey, medication and symptom/AE review, VS, weight

T3 (9 months following surgery): physical exam, measurements, LymQoL survey, medication and symptom/AE review, VS, weight.

T4 (12 months following surgery): physical exam, measurements, LymQoL survey, medication and symptom/AE review, VS, weight, skin punch biopsy (optional for control group), research labs. No compression garment wear x 10 days.

T5 (10 days after T4 visit): measurements, LymQoL survey, medication and symptom/AE review, VS, weight, stitch removal, LSG

T6 (2 years following surgery, BioBridge participants/intervention group): physical exam, medication and symptom/AE review, VS, weight.

T7 (3 years following surgery, BioBridge participants/intervention group): physical exam, medication and symptom/AE review, VS, weight.

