12.4 Primary Analysis

Limb circumference of the affected and unaffected limbs of each participant will be measured for calculation of the volume of the arm through the truncated cone formula.²³ Circumferential measurements of each limb will be obtained with a low stretch gauged tape measure applied at specified intervals of 4 cm (starting from the 3rd metacarpal head) along the axis of the arm, beginning at the wrist. Anatomic landmarks are recorded to facilitate reproducibility between pre- and post-surgical measurements. This method is inexpensive, reproducible, and easily applied. These measurements will be performed at initial evaluation and at each scheduled follow-up visit. The pre-surgical baseline volume for each limb will be defined as the average of the two measurements obtained on study day S1 and study day S2. For quantitative analysis, the excess volume of the limb is defined as the arithmetical difference between the affected

limb (L_{pre}) and the contralateral normal limb (C_{pre}) and the % excess volume at the beginning of the study is defined by:

$$100\% * [(L_{pre} - C_{pre})/C_{pre}].$$

The primary outcome is defined the post-surgical % change in excess limb volume:

$$100 * \{1 - [(L_{post} - C_{post})/(L_{pre} - C_{pre})]\}$$

Analysis Population

Participants are randomized into 1 of 2 arms, the intervention arm (VLNT with BioBridge) or control arm (VLNT-only). The primary analysis will include all participants who have completed all required study visits. However, for participants who do not complete the study, their data will be censored and analyzed with the current population. Treatment summary and adverse event data will also be provided for each treatment category separately.

Efficacy and safety analyses will be performed on all participants who have undergone VLNT (with or without BioBridge). The primary analysis will include all participants who have completed all required study visits and procedures. However participants who do not complete the study will be censored and their data will be analyzed, along with ongoing participants. Data including adverse event data will be captured for each treatment category separately.

Analysis Plan

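### The infection stopping rule does not restrict its count to BioBridge recipients and gives its 10% pause rate no denominator, although about one subject in five never receives the device

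*Combined protocol and SAP*

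**What the plan says.** Section 7.3 of the combined protocol and SAP has two parts. The termination part reads "The study will be terminated if more than 1 of the first 10 subjects experience an infection related to the BioBridge device". The pause part reads "If, after the first 10 subjects are treated, a rate > 10% of BioBridge-related infections is observed, accrual will be paused for a safety review". Neither part limits the subjects to those who received the device, and the second does not say what the rate is divided by.

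Section 3.4 randomizes about 60 subjects 4:1, and "Randomization will be done within blocks (of size 5) so that the balance between treatments is preserved throughout the trial". Section 4 (Study Visits) describes the two groups at surgery: "one with BioBridge scaffold (intervention group), one VLNT only (control group), will occur between S3 and T1 visits". The controls are therefore study subjects who are never exposed to BioBridge.

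Section 12.4 adds that "Data including adverse event data will be captured for each treatment category separately". It does not say how the rule in section 7.3 is to be calculated, and no other section redefines that rule.

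**The concern.** A device-related infection can occur only in a device recipient. If the count runs over all subjects, controls add to the denominator and never to the numerator, so the limit is looser for exposed patients than its wording suggests.

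This is the only numeric safety limit in the documents. Section 7.2 sends serious events of Grade 3 and above to the monitoring committee, and section 11.2 has that committee review serious events. Section 12.2 plans no interim analysis. For a non-serious device infection, section 7.3 is the only stated automatic trigger. Section 7.1 notes that an infection may require revision or removal of the whole matrix. Two careful people applying the rule to the same data could reach different actions.

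**Working it through.** The plan gives no operating characteristics for this rule, so there is no stated figure to reproduce. The detectable difference in section 12.6.2 concerns efficacy and is unaffected.

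**Inputs.** From the documents: 4:1 allocation, blocks of 5, 48 recipients and 12 controls, termination at 2 or more infections in the first 10, pause at a rate strictly above 10%. Assumed: true device-infection rates of 5%, 10% and 15%; one randomization list treated in order; a check after each subject; infections known at once. The documents state no target or unacceptable device-infection rate. Section 4.1 reports post-operative infection below 5% after VLNT, which is not device-specific. On the pilot, section 7.1 says "A total of 55 BioBridge threads were implanted into 8 participants with no reported complications". Zero of 8 has a one-sided exact 95% upper limit of 1 − 0.05^(1/8) = 0.31, so it excludes none of the assumed rates.

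**Exposed patients in the first 10.** Two blocks of 5 give 2 × 4 = 8 recipients and 2 controls. Two infections are 2/8 = 25% of those exposed, against 2/10 = 20% if 10 recipients are counted.

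**Termination probability.** P(at least 2) = 1 − (1 − p)^n − n·p·(1 − p)^(n−1). At p = 0.05:

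- n = 8: 1 − 0.663 − 0.279 = 0.057
- n = 10: 1 − 0.599 − 0.315 = 0.086

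**Infections needed for a rate above 10%.**

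| Subjects treated | Recipients | All-subject denominator | Recipient denominator |
|---|---|---|---|
| 20 | 16 | 3 | 2 |
| 40 | 32 | 5 | 4 |
| 60 | 48 | 7 (7/48 = 14.6% of recipients) | 5 (5/48 = 10.4%) |

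The two counts are equal at subjects 15 and 25. By subject 60 no accrual is left to pause, so the last row shows the drift of the limit rather than a practical trigger.

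**Whole rule, one reading applied throughout.** An exact recursion over 12 permuted blocks of 5 follows recipients, infections and the position of the control. In the all-subject reading, both parts count and divide by all subjects. In the recipient reading, both parts count and divide by recipients, and the pause part starts at recipient 10. Each cell shows all subjects v recipients.

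| True rate | Termination | Pause, never terminated | Any action |
|---|---|---|---|
| 5% | 0.057 v 0.086 | 0.158 v 0.220 | 0.215 v 0.306 |
| 10% | 0.187 v 0.264 | 0.425 v 0.474 | 0.612 v 0.738 |
| 15% | 0.343 v 0.456 | 0.533 v 0.482 | 0.875 v 0.938 |

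Any action is the sum of the two columns before it, up to rounding. At 15% the pause column falls under the recipient reading because more trials terminate.

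**Where the termination counts disagree.** Recipients 9 and 10 fall at subjects 11 to 13. A trial terminated under 10 recipients but not under 10 subjects has its second infection there. The all-subject rate is then between 2/13 = 15.4% and 2/11 = 18.2%, above 10%, so the pause fires anyway.

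**The case against.** The strongest reply is that the documents already lean toward recipients. Only recipients can enter the numerator, section 2.2 describes a BioBridge recipient as treated under the protocol, section 12.4 refers to the BioBridge arm as the treatment arm, and adverse events are captured by treatment category. That makes the recipient reading the more natural one. It does not set the denominator, because treatment category covers both arms and sections 3.4 and 12.1.1 use the word subjects for everyone randomized.

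A reader might infer that one infection at subject 10 already splits the readings: 1/10 = 10.0% (no pause) against 1/8 = 12.5% (pause). A reader might also infer that the denominator alone moves the pause probability at 5% from 0.16 to 0.40. Both come from a mixed reading that starts the rule at 10 subjects of both arms and then divides by recipients only. The text does not exclude it, but it is the least natural reading. If one population is used throughout, one infection in the first 10 is 10% either way and triggers nothing, and the pause contrast at 5% is 0.158 v 0.220.

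Two further objections stand in part. The split of 8 and 2 is exact only for one list treated in order. Section 3.4 does not say the list is central, section 12.6.1 plans three added sites, and the pause part refers to subjects treated; the expected number of controls in the first 10 is still 2. The infection rates are also illustrative, and the 10% and 15% rows are not forecasts.

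**Conclusion.** The point holds as an ambiguity with real but moderate consequences. Followed literally over all subjects, section 7.3 dilutes the only numeric safety limit, and the chance of any action is lower by 0.09 at a 5% true rate (0.306 − 0.215), 0.13 at 10% (0.738 − 0.612) and 0.06 at 15% (0.938 − 0.875). These sizes rest on the assumed rates, a single list treated in order, a check after every subject and immediate knowledge of infections.

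A reader might conclude that the termination wording lets a safety signal go unnoticed. The documents do not support that: in every case where the two termination counts differ, the all-subject pause is triggered. The difference there is between pause-and-review and automatic termination. No efficacy estimate, power figure or analysis is affected.

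**What to change.** Amend section 7.3 in three places:

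- Termination: more than 1 of the first 10 BioBridge recipients.
- Start of the pause part: after the first 10 BioBridge recipients are treated.
- Rate: recipients with a BioBridge-related infection divided by BioBridge recipients treated to date.

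This is a short wording amendment that needs no new data, procedures or sample size. The downside is more action when the true rate is low: at 5%, termination rises from 0.057 to 0.086 and any pause or termination from 0.215 to 0.306. The sponsor and the monitoring committee should confirm that they accept this, or adjust the thresholds, when they settle the denominator.
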